In case of an immediately reportable Adverse Event the investigators can contact the Medtronic Study Manager. Contact details of Medtronic Study Management are given in the Investigational Site File. In case the investigator requires information in a medical emergency situation the investigator can contact the Medical Expert. Contact details of Medical Expert are given in the Investigational Site File.

F.7 Subject accountability

Every subject should be encouraged to remain in the study until they have completed the required follow up per the study protocol. If the subject discontinues prematurely from the study (e.g. withdrawal of the consent, lost to follow-up), the reason for discontinuation must be documented in the subject's hospital record and documented on the appropriate eCRF. Subjects will not be replaced in case of premature study discontinuation.

F.7.1 Criteria and procedures for exit from study

The Study Exit eCRF should be completed after the subject is exited from the study. A subject will be considered to have exited from the study for any of the following reasons:

- Subject completes follow-ups required by the investigational plan
- Subject dies
- Subject requests to be withdrawn
- Investigator requests that subject be withdrawn to protect the welfare of the subject
- Subject is lost to follow-up
- Subject has conversion to open repair
- Other(specify).

F.7.2 Study Withdrawal

Subjects may withdraw from the clinical study at any time and for any reason. If a subject decides to withdraw from the clinical study and agrees to provide the reason for withdrawal, the investigator will document the reason and indicate any relationship of the withdrawal to the study or products being investigated in the subject's hospital record in the subject's file. If discontinuation is because of safety or lack of effectiveness, the subject shall be asked to be followed as per their institution's standard of care outside the clinical study as further described in section F.7.6. In addition, subject withdrawal will be documented on the Study Exit eCRF.

F.7.3 Missed follow-up

A missed follow-up visit should be documented by the investigator and reported in the eCRF including the reason. If the date the subject is last known to be alive is obtained, this should be recorded on the Follow-up visit eCRF and the method of obtaining this date should be documented in the medical record.

F.7.4 Lost-to-follow-up

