8.4. Analysis of the Primary Endpoints

For the primary endpoint, a one-sided 95% confidence interval based on binomial distribution will be constructed in addition to event count and frequency.

The analysis for the regulatory submission will take place when 40 subjects have been implanted with the study device for at least 30 days except that a subject expires early. Endpoints as defined in Section 5 will be analyzed for these 40 ITT subjects.

MAE Rate Calculation:

All MAEs will be adjudicated by the Clinical Event Committee (CEC) per protocol except for the procedural blood loss ≥ 1000 cc, which will be site reported at the index procedure. MAE rate will be calculated as follows (Table 2):

Table 2: MAE Rate Calculation:

MAE rate = $m/(m + k)$	Within 30 Days	Within 183 Days	Within 365 Days
$m = \text{No. of Subjects Who Had MAE(s)}$	No. of subjects who had at least one MAE with onset day from Day 0 to Day 30, inclusive.	No. of subjects who had at least one MAE with onset day from Day 31 to Day 183, inclusive.	No. of subjects who had at least one MAE with onset day from Day 184 to Day 365, inclusive.
$k = \text{No. of Subjects Who Had No MAE}$	No. of subjects who have been in study for at least 1 day and without an MAE.	No. of subjects who have been in study for at least 91 days and without an MAE.	No. of subjects who have been in study for at least 305 days and without an MAE.

If a subject is early terminated from the study, the last day that the subject has been seen will be the duration in study, which can be the day of last follow-up, last imaging taken, an AE reported, or withdrawal from the study. If a subject is still in the study, the duration in study will be the time from index procedure to the cut off day that the database is locked or data snapshot is taken.

Imaging based Event Rate Calculation:

Imaging assessment will be performed by site as well as the core lab. Assessments from the core lab will be analyzed separately from those by site. Imaging based event rate will be calculated using statistical analysis windows as follows (Table 3):

Table 3: Imaging based Event Rate Calculation:

Event rate = m/n	At 1 Month	At 6 Months	At 12 Months
$m = \text{No. of Subjects Who Had Event(s)}$	No. of subjects who had an event with scan day within the 1-month window.	No. of subjects who had an event with scan day within the 6-month window.	No. of subjects who had an event with scan day within the 12-month window.

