8.5. Analysis of the Secondary Endpoints

Descriptive statistical analyses will be performed on secondary endpoints. No inferential statistical analysis is planned for secondary endpoints.

Event rates such as mortality, secondary procedures, serious adverse events, conversion to open surgery, and aneurysm ruptures will be calculated in the same way as the MAE rate, specified in Table 2.

The survival from all-cause and aneurysm-related mortality over one year time or longer will be presented with the Kaplan-Meier survival curve and the associated Kaplan-Meier estimate will be calculated along with its standard error using the Greenwood method.

Imaging based event rate such as stent graft migration, aneurysm expansion, endoleaks, stent graft occlusions, and device deficiencies will be calculated in the way as specified in Table 3.

9. Additional Data Summaries / Supplemental Analyses

Descriptive data summaries will be provided for acute procedural observations and clinical utility measures.

10. Data Screening and Acceptance

Data management will be done according to Medtronic SOPs and the Data Management Plan for this clinical study. These documents will be made available upon request.

All collected data will be reviewed for completeness, correctness and consistency. In case of issues, queries will be sent to the investigator or designee to complete, correct or comment the data.

11. List of Planned Tables, Listings, and Figures

List of planned tables, listing, and figures for the analyses can be found in a separate table shell document.

12. Appendices

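### SAP 8.4 counts an unseen subject as event-free to the data cut if not exited but drops the same subject if exited, so the 183- and 365-day secondary rates depend partly on exit status

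*Protocol*

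**What the plan says.** **Collection.** Protocol F.7.3 (Missed follow-up) states: "If the date the subject is last known to be alive is obtained, this should be recorded on the Follow-up visit eCRF". Collection is conditional on the date being obtained.

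**Duration in study.** SAP 8.4 has two branches.
- Early-terminated subjects: "the last day that the subject has been seen will be the duration in study". Four kinds of date may supply it: a follow-up visit, an image, an AE report or the withdrawal. The F.7.3 date is not listed.
- All others: "If a subject is still in the study, the duration in study will be the time from index procedure to the cut off day" (database lock or snapshot). No contact is required.

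**Denominators.** The Table 2 rate is m/(m + k), where k counts event-free subjects. For the 183-day column k is "No. of subjects who have been in study for at least 91 days and without an MAE". For the 365-day column it is "No. of subjects who have been in study for at least 305 days and without an MAE". For the 30-day column it is "No. of subjects who have been in study for at least 1 day and without an MAE".

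**Scope.** SAP 8.5 extends the Table 2 method beyond MAEs: "Event rates such as mortality, secondary procedures, serious adverse events, conversion to open surgery, and aneurysm ruptures will be calculated in the same way". Kaplan-Meier curves for all-cause and aneurysm-related mortality are planned separately, and no censoring date is given for them.

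**Exit as lost.** Protocol F.7.4 permits, but does not require, a subject to be considered lost after three documented contact attempts, and it sets no deadline. SAP 8.3 has no rule for unknown vital status.

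**The concern.** Take a subject last seen at the 1-month visit who then misses the 6- and 12-month visits. If no exit form has been completed at a snapshot more than 305 days after the procedure, the subject enters k for the 365-day rate as a survivor. If the site has exited the subject as lost, and there is no later image, AE or withdrawal date, the subject is in neither m nor k. The clinical information is the same in both cases. Only the exit status differs, and its timing is left to the site.

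The first branch credits survival that nobody has observed, which can make the event rate too low. The second can discard survival that has been observed. An exited subject last seen on Day 200 but recorded under F.7.3 as alive on Day 400 does not clearly qualify for the 365-day denominator, whereas a known death in the counted period always enters the numerator.

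The SAP asks for more elsewhere: the imaging rates in Table 3 admit a subject to the denominator only with a readable image or an event. The trial is single-arm and descriptive, so these rates are themselves the reported result.

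**Working it through.** **The plan's own figure.** The documents give no precision figure for mortality follow-up. The only computed figure is the margin below 10% for the 30-day MAE rate at 2 of 40 (Protocol C.7, SAP 3.2). The exact one-sided 95% upper limit solves P(X ≤ 2 | n = 40, p) = 0.05, giving p = 14.92%. The margin is 14.92 − 5.00 = 9.92 points, so the figure reproduces and is not in question here.

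**Can scheduled visits produce this situation?** Protocol Table F-1 closes the 1-month window on Day 45 and the 6-month window on Day 213.
- A subject who attends at 1 month and misses the 6-month visit was last at a scheduled visit by Day 45, which is below 91.
- A subject who attends at 6 months and misses the 12-month visit was last at a scheduled visit by Day 213, which is below 305.

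So one missed visit is enough, unless an interim image, AE report or withdrawal date carries the subject past the threshold. An exited subject last seen on Day 320, for example, stays in both denominators.

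**Size of the exit-status effect.** Let N be the subjects, d the deaths counted in the Table 2 column, and u the subjects unseen since before the threshold.
- None of the u exited: d/N
- All of the u exited: d/(N − u)
- Missing-data bound, if all u had died in the counted period: (d + u)/N

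N = 69 is the total enrolment and N = 40 the regulatory cohort. The values of d and u are assumptions; the documents give none.

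| N | d | u | Not exited | Exited | Shift (points) | Bound |
|---|---|---|---|---|---|---|
| 69 | 2 | 1 | 2/69 = 2.90% | 2/68 = 2.94% | 0.04 | 3/69 = 4.35% |
| 69 | 3 | 6 | 3/69 = 4.35% | 3/63 = 4.76% | 0.41 | 9/69 = 13.04% |
| 69 | 4 | 8 | 4/69 = 5.80% | 4/61 = 6.56% | 0.76 | 12/69 = 17.39% |
| 40 | 2 | 4 | 2/40 = 5.00% | 2/36 = 5.56% | 0.56 | 6/40 = 15.00% |
| 40 | 2 | 8 | 2/40 = 5.00% | 2/32 = 6.25% | 1.25 | 10/40 = 25.00% |

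For N = 69, d from 2 to 4 and u from 1 to 8, the shift runs from 0.04 to 0.76 points. It can pass 1 point in the 40-subject cohort, but only with a fifth of subjects unseen.

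**Effect of using the F.7.3 date.** With N = 69, d = 3 and u = 6, let v of the six be documented alive on Day 305 or later. The rate is 3/(63 + v): 4.76% at v = 0, 3/66 = 4.55% at v = 3, and 4.35% at v = 6. It is one value whatever the exit status.

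**Kaplan-Meier, only if the same duration rule sets the censoring times.** Assume 69 subjects, deaths on Days 100, 250 and 330, and six subjects unseen after Day 183. Censored at the cut, one-year survival is 66/69 = 95.65%. Censored at last day seen, it is (68/69) × (60/62) = 95.37%. The difference is 0.28 points.

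**30-day rate.** Its threshold is 1 day in study, so exit status has almost no influence on it.

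**The case against.** The strongest reply is proportionality. These are secondary, descriptive endpoints with no hypothesis or threshold, and exit status alone moves them little. Lost to follow-up is a listed exit reason (Protocol F.7.1), and all data must be entered and approved before close-out (G.4), so the open-ended branch matters mainly at snapshots. Missed visits are reported with reasons and count as deviations, sponsor calls check event reporting, and subject accountability is summarised. All of this stands and limits the severity. It makes unseen subjects visible but does not change the denominator.

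A second reply is that the qualifying dates are introduced permissively and include the last follow-up and withdrawal. Because the F.7.3 date is recorded on the follow-up visit form, it might be read as a follow-up date. That is possible, but the rule turns on when the subject was seen, so the SAP should settle it.

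A reader might also infer more than the documents support:
- *That 5-year mortality proportions are distorted in the same way.* Table 2 has no column beyond 365 days. Longer-term mortality is planned as Kaplan-Meier, where an exited subject would be censored, not dropped.
- *That the Kaplan-Meier curve is biased.* The duration rule sits under the MAE rate calculation and no censoring date is stated for the curve. Applying the rule there is an inference. Earlier censoring, if non-informative, costs precision and does not bias.
- *That the bounds of 13% to 25% measure the error.* They assume every unseen subject died and reflect missing data. A last-known-alive date narrows them only where one was obtained.
- *That F.7.3 is defective.* It is not; the gap is in the SAP.

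**Conclusion.** The point holds for the 183- and 365-day mortality and other event rates calculated by the Table 2 method. As written, SAP 8.4 gives two answers for the same unseen subject, and one of them counts the subject as event-free without any contact. The documented alive date that could often resolve this is not named in the rule.

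The exit-status shift is under 1 percentage point for 69 subjects at the assumed counts of 2 to 4 deaths and 1 to 8 unseen. The larger weakness is that survival is credited without evidence, and its size cannot be known from the documents. The illustrations take d as the deaths the relevant Table 2 column counts; that table's onset-day intervals are a separate matter.

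The 30-day primary safety endpoint and the sample-size reasoning are essentially unaffected. Any effect on Kaplan-Meier is conditional on the same rule being used. The correction is inexpensive and worth making, at a priority between optional and recommended.

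**What to change.** In SAP 8.4, use one end-of-follow-up rule regardless of exit status.
- **Mortality:** a subject without the event enters the denominator only if the latest documented alive date reaches the Table 2 threshold. Qualifying dates are a visit, an image, an AE report, a withdrawal contact, or the F.7.3 last-known-alive date.
- **Non-fatal events:** use the last AE assessment or contact in place of the alive date.
- **Kaplan-Meier (SAP 8.5):** state that subjects are censored at the latest documented alive date.
- **Reporting:** give the number with unknown vital status at each time point.

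The cost is a few sentences of SAP text and a small programming change; the data field already exists. There is a downside to acknowledge. At a snapshot, subjects between visits will have slightly shorter follow-up. Deaths, as serious adverse events, reach the sponsor within 3 calendar days of the investigator learning of them (Protocol Table F-4), so estimated mortality there may be slightly higher. The rule also cannot recover vital status where no alive date was obtained, which is why the unknown count should be shown.

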The primary safety endpoint is defined as the proportion of subjects experiencing a MAE within 30 days post-implantation. MAEs include the occurrence of any of the following events:

- All-cause mortality
- Bowel ischemia
- Myocardial infarction
- Paraplegia
- Procedural blood loss ≥ 1000 cc
- Renal failure
- Respiratory failure
- Stroke

Detailed definitions of MAEs are provided in Appendix L.2.

C.2.1.2 Primary Effectiveness Endpoint

Technical success at the index procedure (as assessed intra-operatively) is defined as successful delivery and deployment of the Endurant Evo AAA Stent graft system in the planned location and with no unintentional coverage of both internal iliac arteries or any visceral aortic branches and with successful removal of the delivery system

C.2.2 Secondary Endpoints

The following secondary endpoints will be evaluated:

- All cause-mortality within 30, 183, and 365 days
- Aneurysm-related mortality within 30, 183, and 365 days
- Secondary procedures to correct Type I and III endoleaks within 30, 183 and 365 days
- Secondary endovascular procedures within 30, 183 and 365 days
- Serious adverse events within 30, 183 and 365 days
- Aneurysm rupture within 30, 183 and 365 days
- Conversion to open surgery within 30, 183 and 365 days
- Major adverse events within 183 and 365 days
- Stent graft migration at 12-month follow-up visit (as compared to 1-month imaging)
- Aneurysm expansion > 5 mm at 12-month follow-up visit (as compared to 1-month imaging)
- All endoleaks based on imaging findings at 1- month, 6-month and 12-month visits
- Stent graft occlusion based on imaging findings through 6 months and 12 months

Device deficiencies based on imaging findings through 6 months and 12 months Secondary endpoints will be assessed at annual follow-up visits until 5 years post-implantation Detailed definitions for secondary endpoints are provided in Appendix L.2.

C.3 Study Hypothesis

The Endurant Evo International Clinical Trial is not hypothesis driven; all endpoints will be analyzed descriptively.

Endurant Evo is a next generation abdominal low profile stent graft system on the Endurant product platform. The safety and performance of the commercially available Endurant and Endurant II devices have been well established. As such, this trial is not designed to make a statistical comparison, but rather to collect data demonstrating that the Endurant Evo system performs as expected clinically.

C.4 Study population

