NOTE 2: This definition includes any event resulting from use error or from intentional misuse of the investigational medical device.

Serious Adverse Event (SAE): (ISO 14155:2011 3.37)

Adverse event that

- a) led to death,
- b) led to serious deterioration in the health of the subject, that either resulted in
 - 1) a life-threatening illness or injury, or
 - 2) a permanent impairment of a body structure or a body function, or
 - 3) in-patient or prolonged hospitalization, or
 - 4) medical or surgical intervention to prevent life-threatening illness or injury or permanent impairment to a body structure or a body function,
- c) led to fetal distress, fetal death or a congenital abnormality or birth defect.

NOTE: Planned hospitalization for a pre-existing condition, or a procedure required by the CIP, without serious deterioration in health, is not considered a serious adverse event.

Serious Adverse Device Effect (SADE): (ISO 14155:2011 3.36)

Adverse device effect that has resulted in any of the consequences characteristic of a Serious Adverse Event.

Unanticipated Serious Adverse Device Effect (USADE): (ISO 14155:2011 3.42)

Serious adverse device effect which by its nature, incidence, severity or outcome has not been identified in the current version of the risk analysis report.

NOTE: Anticipated serious adverse device effect (ASADE) is an effect which by its nature, incidence, severity or outcome has been identified in the risk analysis report.

Device deficiency: (ISO 14155:2011 3.15)

Inadequacy of a medical device with respect to its identity, quality, durability, reliability, safety or performance.

NOTE: Device deficiencies include malfunctions, use errors, and inadequate labelling.

F.6.2 Recording and reporting of Adverse Events

Adverse Event (AE) information will be collected throughout the study and reported to Medtronic on the Adverse Event eCRF. The investigator is responsible for reporting all AEs as reportable/collectable per CIP to Medtronic. See the Adverse Event eCRF for the information to be reported for each Adverse Event. Please see guidance for reporting of Adverse Events following image review in Appendix L.5.

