A subject may be considered lost to follow-up once the investigator and/or research staff has made three documented attempts to contact the subject. The third attempt should be made by certified mail to the subject.

F.7.5 Conversion to open repair

If a primary conversion to open repair is required during the index procedure, then the subject will be followed for 1 month, at which time the subject will be exited from the study.

If a secondary conversion to open repair is required during the follow-up period, then the subject will be followed for 30 days after the conversion, at which time the subject will be exited from the study.

F.7.6 Medical care after study exit

After study exit the subjects will be followed as per routine standard of care by the investigational site or a treating physician which might be in line with the guidelines described in the *Management of Abdominal Aortic Aneurysms Clinical Practice Guidelines of the European Society for Vascular Surgery*¹⁹ or *Society for Vascular Surgery practice guidelines for the care of patients with an abdominal aorticaneurysm*²⁰.

Relevant medical records may be made available by the investigational sites for the treating physician per local laws and regulations if needed for further subject treatment. As per local law and regulation the trial investigator may be contacted by the treating physician in case of questions related to the study device and treatment.

F.8 Study/Protocol deviations and CIP changes

A study deviation is an event where the investigator or investigation site personnel did not conduct the clinical study according to the clinical investigation plan or clinical trial agreement. The investigator is not allowed to deviate from the above mentioned documents except with prior approval and/ or under emergency circumstances. All deviations shall be documented and explained, regardless of the reason for the deviation.

Specific examples of deviations include but are not limited to:

- Failure to obtain informed consent prior to participation
- Incorrect version of the informed consent form used
- No EC approval before the start of the study
- Enrolled subject did not meet inclusion/exclusion criteria
- CIP required testing and/or measurements not done or incorrectly done subject did not attend follow up visit or follow up visit outside window
- Unauthorized use of investigational devices
- Adverse event not reported by investigators in the required time frame as specified in the CIP

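### Three unanswered contact attempts can end a consenting subject's participation, and neither document says what happens to late events if that subject returns

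*Protocol*

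**What the plan says.** - **Trigger (Protocol F.7.4).** "A subject may be considered lost to follow-up once the investigator and/or research staff has made three documented attempts to contact the subject". The next sentence adds: "The third attempt should be made by certified mail to the subject". Nothing is said about elapsed time, spacing of attempts, number of missed visits, or a check of hospital records or vital status.
- **Consequence (F.7.1).** "A subject will be considered to have exited from the study for any of the following reasons"; the list includes "Subject is lost to follow-up".
- **Missed visits (F.7.3).** "A missed follow-up visit should be documented by the investigator and reported in the eCRF including the reason". A last-known-alive date is recorded if obtained. A missed visit is not itself an exit reason, and no rule says when F.7.3 gives way to F.7.4.
- **After exit (F.7.6).** "After study exit the subjects will be followed as per routine standard of care by the investigational site or a treating physician". No section describes re-entry or study data collection after exit.
- **Collection period (F.6.2).** "Adverse Event (AE) information will be collected throughout the study". Whether an exited subject still counts as in the study is not addressed.
- **Horizon (C.2.2).** "Secondary endpoints will be assessed at annual follow-up visits until 5 years post-implantation".
- **SAP 8.3, 8.4 and 8.5.** Only incomplete onset or death dates are imputed. Time in study stops at the last contact for a subject who left early, but runs to the data cut-off for one who has not left. Table 2 computes m/(m + k), where m counts subjects with an event onset in the column's day range and k counts event-free subjects with enough time in study. Section 8.5 applies the same method to mortality, secondary procedures, serious adverse events, conversion and rupture.

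**The concern.** A subject who does not answer two contacts and a certified letter has not refused anything. The text nevertheless lets the site close that subject's participation, possibly around the 6- or 12-month visit with years of follow-up left. Two sites could handle the same non-responder differently, one under F.7.3 and one under F.7.4, and both would comply.

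Protocol J.3 says the observed device deficiencies indicate higher risk than with other commercially available devices, that enrollment has ended, and that follow-up continues. What the trial can still deliver is long-term device safety in 69 subjects. A former non-responder who comes back to the implanting hospital because of a rupture, a re-intervention or a stent failure is among the most informative subjects, and the plan does not secure that observation. Routine in-person monitoring has been replaced by telephone and email contact (G.2), so such an event is less likely to be found by chance.

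**Working it through.** The documents give no loss-to-follow-up rate, so there is no plan figure on this point to reproduce. The only sample-size figure, a margin below 10% for 2/40, does reproduce (exact one-sided 95% upper limit 14.92%, margin 9.92 points) and does not depend on this issue. Everything below is illustration under stated assumptions.

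**1. How many subjects could be exited.** Inputs: 69 enrolled (Protocol C.5); seven scheduled visits (Table F-1), of which three fall in years 3-5, the remaining follow-up addressed in F.6. Assume that 2% to 5% of subjects per visit do not answer three attempts and that every such subject is exited.

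| Visits | Formula | 2% | 5% |
|---|---|---|---|
| Years 3-5 | 1 − (1 − r)^3 | 5.9% (about 4 of 69) | 14.3% (about 10 of 69) |
| All seven | 1 − (1 − r)^7 | 13.2% (about 9 of 69) | 30.2% (about 21 of 69) |

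These are upper illustrations, because the rule is permissive. If non-response were only a missed visit, independent between visits, 2% to 5% (about 1 to 3 subjects) would be missing at the 5-year visit.

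**2. What unrecorded events do to a rate.** Use m/(m + k), extending Table 2 to a late time point. Assume 3 events observed, 2 more among exited subjects, and all exits early enough to fall out of k.

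| Exited | Late events not recorded | Late events recorded | All 69 known, other exited subjects event-free |
|---|---|---|---|
| 3 | 3/66 = 4.5% | 5/68 = 7.4% | 5/69 = 7.2% |
| 14 | 3/55 = 5.5% | 5/57 = 8.8% | 5/69 = 7.2% |

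With no events observed and one missed, 3 exits give 0/66 (one-sided 95% upper limit 4.4%) instead of 1/67 = 1.5% (upper limit 6.9%). The last column of the table shows that adding only returning subjects can overshoot when many are lost, because event-free lost subjects do not return to k.

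**3. Subjects lost late in an interval.** Table 2 accepts 305 days in study as event-free at 365 days, and 91 days at 183 days. A subject last seen just after such a day stays in k, so an unrecorded event later in that interval lowers the rate by up to 1/69 = 1.4 points.

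**4. Why delaying exit alone would do harm.** Take 21 of 69 non-responders and 3 observed events. If they are exited before the threshold, m = 3 and k = 45, giving 3/48 = 6.3%. If they stay formally open, SAP 8.4 runs their time in study to the data cut-off, so k = 66 and the rate is 3/69 = 4.3%. Those 21 people were not seen, yet they count as event-free.

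**The case against.** A reader might infer that one missed visit triggers permanent exit, that F.7.4 overrides F.7.3, or that events after exit are discarded. The documents do not support this. F.7.4 is permissive and does not mention a single missed visit. Neither document calls the exit permanent, bars re-entry or forbids recording a later event, and data collected before exit are not removed. The numerator in SAP Table 2 has no in-study condition, so a later event that was reported could be counted.

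Other provisions may catch such events. Table F-4 starts the reporting clock when the investigator learns of an event or deficiency. F.6.3 makes the investigator responsible for all device deficiencies. F.3 sends unscheduled stent-graft imaging to the core lab. F.8 treats a missed visit as a deviation. None of these expressly covers exited subjects, but none excludes them. The monitoring, data management and safety plans are not available here and may say more.

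It is also fair that a smaller denominator does not by itself lower a rate. Low bias needs events to be more frequent among exited subjects than among those retained. The 69 may include subjects who leave after one month by design (F.1, F.2.1.2). All endpoints are descriptive.

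The strongest objection is that keeping non-responders open without touching SAP 8.4 biases rates low, as step 4 of the check shows. It stands in full and shapes the fix. What survives on the other side is the gap itself: no threshold before exit, no reinstatement, and no stated duty to record later events.

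**Conclusion.** The concern holds as a gap in the exit rule. A consenting subject may be exited after three contact attempts, possibly around one missed visit, and late events in that subject may go unrecorded because both documents are silent on return. That they must go unrecorded cannot be concluded.

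The size is unknown. With assumed non-response of 2% to 5% per visit, and every non-response treated as an exit, about 4 to 10 of 69 subjects would be affected over the year 3-5 visits, or 9 to 21 over all seven. The effect on rates depends on whether exited subjects have more events than retained ones, which the documents cannot tell us.

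The exposure is confined to the longer-term secondary endpoints. Technical success is judged during the procedure, and the 30-day MAE rate is touched only by loss before Day 30. The change is worth making because late device safety is what the trial can still deliver.

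**What to change.** **Protocol F.7.4 and F.7.1.**
- Record non-response as a missed visit under F.7.3 and repeat the contact attempts in each later visit window.
- Make lost to follow-up final only when the 60-month window closes (Day 1882, Table F-1).
- State that a subject who re-presents before then resumes data collection.
- At each missed window, have the site check its own records for vital status and aortic procedures, as consent and local law allow.

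**SAP 8.4, in the same amendment.** End time in study for any subject not currently being seen on the last day seen or the last day of confirmed status, not at the data cut-off, so that unseen subjects do not enter k as event-free. Report how many late events were found only through re-presentation.

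**Cost.** A few extra contacts and record checks per non-responder, protocol wording and a one-line SAP change; no added visits or subjects. Two limits remain. A site's own records will not show events treated elsewhere. Subjects who return because of an event may be over-represented, which errs on the conservative side for safety; the requested count lets a reader judge by how much.
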